- Is there a reduced ability to maintain and shift attention?

Feature 3. Disorganized Thinking

- Was the patient's thinking disorganized or incoherent, such as rambling or irrelevant conversation, unclear or illogical flow of ideas, or unpredictable switching from subject to subject?
- Was the patient able to follow questions and commands throughout the assessment?

Feature 4. Altered Level of Consciousness

- Any level of consciousness other than 'alert'.
- Alert-normal, spontaneous fully aware of environment and interacts appropriately.
- Vigilant-hyperalert
- Lethargic-drowsy but easily aroused, unaware of some elements in the environment, or not spontaneously interacting appropriately with the interviewer; becomes fully aware and appropriately interactive when prodded minimally
- Stupor-difficult to arouse, unaware of some or all elements in the environment, or not spontaneously interacting with the interviewer; becomes incompletely aware and inappropriately interactive when prodded strongly
- Coma – unarousable, unaware of all elements in the environment, with no spontaneous interaction or awareness of the interviewer, so that the interview is difficult or impossible event with maximal prodding

7. ICU Length of stay [Time Frame: ICU stay]

ICU length of stay is calculated from time of ICU admission to time and date of actual discharge.

To be assessed up to ICU discharge.

8. Hospital Re-admission Rates [Time Frame: 6-months]

To be assessed up to 6-months post-surgery. Count and proportion of patients who were admitted to hospital more than once.

9. Hospital Length of stay [Time Frame: hospitalization]

Hospital length of stay will be calculated from the date of index surgical procedure to time and date of discharge from hospital.

To be assessed up to hospital discharge.

10. 6-Month Survival [Time Frame: 6-months]

Kaplan-Meier curves of and hazard ratio of survival over 6 months starting with day of surgery.

11. Quality of Life [Time Frame: day 30, 3-months and 6-months]

The SF-36 physical and mental summary scales will be analyzed separately.

Barthel Index of Activities of Daily Living Total Score

Frailty Scale

12. Return to work [Time Frame: 6-months]

Assessed using a questionnaire to determine the patient's ability to return to their pre-operative working capabilities. To be assessed up to 6 months post-surgery.

13. 6-minute walking test [Time Frame: hospital discharge]

This was done in a sub-study of pre specified patients.

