6.2.2 Secondary outcomes

Secondary binary outcomes such as cardiovascular complications, postoperative delirium, re-admissions, hospital-acquired infections and 30-day mortality will be compared between groups by a logistic mixed effects model with site included as a random effect.¹ Odds ratios with 95% confidence intervals will be reported.

Six-month mortality will be described by group using Kaplan-Meier curves. Survival will be compared by a hazard ratio with 95% confidence intervals and corresponding Wald test. Estimates will be derived from the Cox proportional hazards model with a random frailty for site. If the proportional hazards assumption is clearly and meaningfully violated, we will report a smoothed time dependent hazard ratio over time. However, the aforementioned overall Wald test will remain the primary test of statistical significance. Patients will be censored at the earliest of 183 days post randomization or last known follow-up.

Length of ICU and hospital stay will be summarized by arm using the quartiles of time to live discharge estimated from the subdistribution cumulative incidence function (CIF) where death is treated as a competing risk precluding the possibility of discharge. The between arm difference in time to live discharge will be tested using the Wald test from the Cox proportional hazards model with site as a random frailty to account for potential between site heterogeneity. Patients who die prior to discharge will be censored after the end of the follow-up period to account for the competing risk of death. This will yield virtually the same results as the Fine and Gray approach treating death as a competing risk precluding discharge, except we will have incorporated ICU as a random effect. This outcome is also known as time-to-discharge-alive (TTDA).

The SF-36, Barthel Index and frailty scale will be collected at baseline. At 30 days, 3 months and 6 months after surgery, we will repeat the Barthel Index and SF-36 and collect return to work data. The SF-36 physical and mental summary scales and the Barthel index will be treated as continuous variables and analyzed using a linear mixed effects model for longitudinal data. In order to include all patients

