6.2.6 Subgroup analysis

A priori, we expect that there may be a heterogeneity of treatment effect amongst different patient populations. For example, older, sicker patients with less reserve may benefit the most from selenium supplementation. Thus, we plan to do a subgroup analysis comparing the treatment effect in older patients vs. younger patients (based on median age of 70), patients who are frail (Clinical Frailty Scale ≥ 4)⁵ vs. those who are not, patients who are at nutrition risk (positive features of reduced oral intake or recent weight loss) vs. those that are not, in patients that undergo combined procedures (CABG+ value(s) and CABG plus 'other') vs. those that do not have combined procedures, patients who underwent urgent surgery vs. those who underwent elective surgery, patients with moderate-severe baseline chronic kidney disease vs. those that do not, patients with a low ejection fraction (EF <39%) vs. those with EF 40 or greater, and patients with a higher vs lower Euroscore (based on the median score)

and longer vs. shorter CPB (based on median value). In support of these proposed analyses, there is an apparent decline in circulating selenium levels in the elderly in certain populations, which may occur independently of intake.^{6,7} Given the potential differences in baseline selenium levels between North Americans and Europeans (due to selenium depletion in the soil in Europe),⁸ we plan to compare the effect of selenium in the Canadian vs. German subpopulations. Forest plots will be provided to display the effect measure with 95% CIs within each subgroup and sites. For these subgroup analyses, we plan to examine the primary outcome and select secondary outcomes (TTDA, 6 month survival and DAPHD6M). The effect measure for the primary outcome will be the stratified c-index as described in section 6.2. Statistical tests of interaction between treatment arm and subgroup may be performed if treatment effect appears meaningfully different between subgroups.

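### Interaction tests are run only where the subgroup results already look different, so the reported p-values are a result-selected set; the ejection-fraction cuts also leave a gap

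*SAP*

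**What the plan says.** Section 6.2.6 lists ten two-way splits: age, frailty, nutrition risk, combined procedure, urgency, chronic kidney disease, ejection fraction, EuroSCORE, bypass time and country. On outcomes it says "we plan to examine the primary outcome and select secondary outcomes (TTDA, 6 month survival and DAPHD6M". On display it commits without condition: "Forest plots will be provided to display the effect measure with 95% CIs within each subgroup and sites". On testing it does not commit: "Statistical tests of interaction between treatment arm and subgroup may be performed if treatment effect appears meaningfully different between subgroups". It gives no threshold for that judgement and no method for the test.

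Other sections that bear on this:

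- Section 6.2.2 introduces TTDA with "Length of ICU and hospital stay will be summarized by arm using the quartiles of time to live discharge" and ends the paragraph with "This outcome is also known as time-to-discharge-alive (TTDA". Section 6.1.2 treats the two stays as separate outcomes with different starting points. Item 7: "ICU length of stay is calculated from time of ICU admission to time and date of actual discharge". Item 9: "Hospital length of stay will be calculated from the date of index surgical procedure to time and date of discharge from hospital".
- The ejection-fraction split is "patients with a low ejection fraction (EF <39%) vs. those with EF 40 or greater".
- Section 5.1 leaves p-values unadjusted and handles multiplicity of secondary outcomes by interpretation.
- Section 6.2.4 allows control for site and nothing else.
- Section 1.1 records that no outcome results by arm had been generated when version 1 was finalized.

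**The concern.** The interaction is the formal comparison of treatment effects that section 6.2.6 sets out to make, yet it is the one element decided after the arms have been compared. Two analysts following the same text could report different sets of tests. Any p-value that appears has already passed an unrecorded screen on the quantity it tests, so it cannot be read as an ordinary p-value. Section 6.2.6 predicts more benefit in older, sicker patients and a possible difference between Canada and Germany, so an interaction p-value there will attract attention.

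Setting results against the number of tests requires knowing that number. Here the data determine how many tests are run, and the text leaves the maximum uncertain because TTDA may mean one outcome or two.

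The ejection-fraction gap is a separate and smaller matter: patients in it drop out of that one comparison.

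**Working it through.** The SAP states no figure on this point, so there is none to reproduce. The checks below measure the consequence.

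**1. Effect of the screen.** Let z be the standardized interaction estimate, standard normal when there is no interaction. Suppose a test is run only if |z| > c, with c < 1.96. Every result with p<0.05 passes the screen, so

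P(p<0.05 | run) = 0.05 / P(|Z| > c).

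The SAP gives no c, so the values below are assumed.

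| Assumed c | P(test run) | P(p<0.05, given run) | Expected tests run, of 40 |
|---|---|---|---|
| 0.5 | 0.617 | 0.05/0.617 = 0.081 | 24.7 |
| 1.0 | 0.317 | 0.05/0.317 = 0.158 | 12.7 |
| 1.5 | 0.134 | 0.05/0.134 = 0.374 | 5.3 |

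The joint probability that a test is run and is significant stays at 0.05 in each row, provided every test that passes the screen is run. The selection therefore inflates the false-positive share among reported tests, not the rate per factor.

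**2. Number of possible tests.**

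- TTDA counted once: 10 factors × 4 outcomes = 40 tests; 40 × 0.05 = 2.0 expected at p<0.05 by chance.
- TTDA for both ICU and hospital stay: 10 × 5 = 50 tests; 50 × 0.05 = 2.5.

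These expectations do not require independent tests.

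**3. Power of an interaction test on PODS-free days (PFDs).** Take at face value the 90% power at two-sided 0.05 in section 4.3. The design effect is then 1.960 + 1.282 = 3.24 overall standard errors. For subgroups holding shares p and 1−p of the patients,

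SE(interaction) = SE(overall) × √(1/p + 1/(1−p)) = SE(overall) / √(p(1−p)).

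For an interaction as large as the whole design effect:

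- 50:50 split: z = 3.24 × 0.500 = 1.62; power = P(|Z + 1.62| > 1.96) = 0.367.
- 25:75 split: z = 3.24 × 0.433 = 1.40; power = 0.289.

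The splits are assumed. Power is the same with or without the screen; it matters for how a non-significant result may be read.

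**4. Ejection fraction.** Under the written cuts, 38 and 38.9 are low; 39, 39.5 and 39.9 are in neither group; 40 and 41 are in the upper group. If values are recorded in whole percent, only 39 is lost. The SAP gives no count. Each 1% of the planned 1400 patients falling in the gap would be 0.01 × 1400 = 14 patients.

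**5. Does the proposed interaction test for the c-index hold its level?** It was simulated with no effect: 2,000 trials per setting, 400 bootstrap samples each drawn within site and arm, and about 1400 patients in 20 sites. Simulated PFDs had mean 23.3, SD 8.5 and 10% zeros, against 23.2, 9.2 and 4% + 6% in section 4.3.

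| Sites | Split | Rejection, estimate / bootstrap SE | Percentile interval excludes 0 |
|---|---|---|---|
| Equal, 70 each | 50:50 | 4.6% | 5.0% |
| Equal, 70 each | 25:75 | 5.2% | 5.4% |
| Sizes 14 to 194 | 50:50 | 5.3% | 5.7% |
| Sizes 14 to 194 | 25:75 | 5.2% | 5.5% |

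With 2,000 trials the simulation standard error is √(0.05 × 0.95 / 2000), or 0.5 percentage points, so all eight figures are compatible with a level close to 5%.

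**The case against.** The strongest reply concerns weight. The factors and outcomes are listed in advance, and every subgroup estimate is shown with its interval whatever the result. A reader can approximate an untested interaction from the forest plot and use the full list as the denominator. Neither the primary test nor the error rate per factor is affected. All of this stands, and it limits the point to the selective display of exploratory p-values. It does not remove the point: separate subgroup intervals are not an interaction estimate, and formal p-values would still appear only where the contrast looked large.

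The assumed |z| thresholds are also open to challenge. The SAP's phrase more naturally refers to the size of the effect, and an effect-size screen would correspond to a different |z| for each factor and outcome. That is fair: the 8%, 16% and 37% show direction and range and are not predictions for this trial. Section 5.1 speaks of secondary outcomes and sets no explicit rule for subgroup tests, so its protection here is indirect at best.

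Against the remedy, a percentile interval paired with a p-value from estimate over standard error can occasionally disagree. This is true, but the simulated rejection rates differ by at most 0.4 percentage points, and section 6.2.1 already pairs a van Elteren p-value with a percentile bootstrap interval.

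Finally, the analytic dictionary mentioned in section 6.1.4 may settle the ejection-fraction coding. The SAP text does not.

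**Conclusion.** The concern holds. As written, the plan yields a set of interaction p-values chosen by the results they test, with an undefined trigger and an unsettled maximum of 40 or 50. Among null tests actually run, the share reaching p<0.05 exceeds 5% under any screen that favours larger observed differences; how far it exceeds 5% depends on a trigger that the SAP does not state. The reach is limited to exploratory subgroup claims, and the single primary test is unaffected. The ejection-fraction gap is certain on the text, concerns one of the ten comparisons, and is of unknown size. The plan should be changed on both counts, but neither threatens the trial's main conclusion.

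**What to change.** Replace the conditional sentence in section 6.2.6 with:

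> For each of the ten listed subgroup factors and each listed outcome, the treatment-by-subgroup interaction will be estimated and reported with its 95% CI and an exploratory, unadjusted p-value, regardless of the observed pattern. The number of interaction tests, and the number expected to reach p<0.05 by chance (5% of that number), will be stated beside them. A non-significant interaction will not be read as evidence of a homogeneous effect.

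Also:

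- **TTDA.** State whether the subgroup analysis uses ICU stay, hospital stay or both. This fixes the count at 40 (about 2 expected by chance) or 50 (about 2.5).
- **PFDs and days alive post discharge (DAPHD6M).** Use the difference between the two subgroups' within-site c-indexes, with a percentile interval from 10,000 bootstrap samples drawn within site and arm, and a two-sided p-value from the difference divided by its bootstrap standard error.
- **TTDA and 6-month survival.** Use the planned Cox model with site frailty, adding the subgroup main effect and its interaction with treatment.
- **Section 6.2.4.** Add that the subgroup main effect enters these interaction models only. This is a clarification, since the present wording admits no covariate but site.
- **Ejection fraction.** Make the two categories share one boundary. The trial team should reconcile which boundary was meant.

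The cost is a formal revision of a finalized version 1, modest programming on models already planned, and a table of 40 to 50 low-powered exploratory p-values. The revision should be dated before any by-arm results are generated.

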6.3 Missing Data

The number of missing items will be presented by arm for each outcome. For the primary outcome, if >5% of patients have missing values then we will perform multiple imputation based on prior daily data and baseline characteristics to use the entire mITT population for the primary analysis of the primary outcome.

6.4 Additional analysis

The database generated from the SUSTAIN CSX trial may be used for additional secondary analyses exploring questions other than assessing the efficacy Sodium Selenite Administration in high-risk cardiac surgical patients undergoing complicated open-heart surgery. Plans for these additional secondary analyses are to be determined and are not part of the primary SUSTAIN CSX analysis.

6.5 Statistical Software

The main analysis was performed using SAS 9.4 TS level 1M2 and SAS/STAT version 14.2 under Windows 7 Professional version 6.1.7601. The independent validation of selected items (see section 8.2) was performed using the same software and operating system except SAS 9.4 was level 1M4.

7 Quality assurance

7.1 Data quality

Data was entered into REDCap by trained local site personal. Each user with access to REDCap had a unique username and password. Access to REDCap was secure and an audit trail was maintained to keep track of the username, time, and values of all data entry and modification. A custom secure randomization module was used to implement the randomization list and maintain concealment of future allocations. A custom query module was used to implement extensive value, range, logical

(including date sequence) data checks. Any violation of the pre-defined data checks triggered data queries that were tracked and required resolution (either correction or acceptance by central staff) prior to data being marked as finalized.

A touch base meeting was conducted with each site after their first patient to address any questions that may have arose in conducting the study and collecting data. Key data items from 2 patients at each site were monitored via source verification once they had randomized 2 patients. After the initial 2 patients were monitored, sites were assessed for risk and follow-up monitoring only conducted when needed. The REDCap database was downloaded and converted into a multi-table analytic SAS database. Some filtering, data transformation, and variable derivation was performed in SAS. Boxplots were generated for all continuous variables and outliers were queried; all outliers were either corrected or verified as correct.

Quality assurance reports were run periodically throughout the trial to assess the completeness, timeliness, validity and quality of trial implementation and data capture by site. Issues were flagged and resolved with participating sites in real time.

Trial and Trial registration	1a	Descriptive title that matches the protocol, with SAP either as a forerunner or subtitle, and trial acronym (if applicable)	1
	1b	Trial registration number	1
SAP Version	2	SAP version number with dates	1
Protocol Version	3	Reference to version of protocol being used	1
SAP revisions	4a	SAP revision history	1
	4b	Justification for each SAP revision	1
	4c	Timing of SAP revisions in relation to interim analyses, etc.	1
Roles and responsibility	5	Names, affiliations, and roles of SAP contributors	2
Signatures of:	6a	Person writing the SAP	1, 3
	6b	Senior statistician responsible	1
	6c	Chief investigator/clinical lead	1
Section 2: Introduction			
Background and rationale	7	Synopsis of trial background and rationale including a brief description of research question and brief justification for undertaking the trial	6
Objectives	8	Description of specific objectives or hypotheses	6
Section 3: Study Methods			
Trial design	9	Brief description of trial design including type of trial (e.g., parallel group, multi-arm, crossover, factorial) and allocation ratio and may include brief description of interventions	6
Randomization	10	Randomization details, e.g., whether any minimization or stratification	6

		occurred (including stratifying factors used or the location of that information if it is not held within the SAP)	
Sample size	11	Full sample size calculation or reference to sample size calculation in protocol (instead of replication in SAP)	7
Framework	12	Superiority, equivalence, or noninferiority hypothesis testing framework, including which comparisons will be presented on this basis	7
Statistical interim analysis and stopping guidance	13a	Information on interim analyses specifying what interim analyses will be carried out and listing of time points	8
	13b	Any planned adjustment of the significance level due to interim analysis	NA
	13c	Details of guidelines for stopping the trial early	NA
Timing of final analysis	14	Timing of final analysis, e.g., all outcomes analysed collectively or timing stratified by planned length of follow-up	8
Timing of outcome assessments	15	Time points at which the outcomes are measured including visit “windows”	8
Section 4: Statistical Principals			
Confidence intervals and P values	16	Level of statistical significance	8
	17	Description and rationale for any adjustment for multiplicity and, if so, detailing how the type 1 error is to be controlled	8
	18	Confidence intervals to be reported	8
Adherence and Protocol deviations	19a	Definition of adherence to the intervention and how this is assessed including extent of exposure	8
	19b	Description of how adherence to the intervention will be presented	13
	19c	Definition of protocol deviations for the trial	NA
	19d	Description of which protocol deviations will be summarized	NA

Analysis populations	20	Definition of analysis populations, e.g., intention to treat, per protocol, complete case, safety	8
Section 5: Trial Population			
Screening data	21	Reporting of screening data (if collected) to describe representativeness of trial sample	8
Eligibility	22	Summary of eligibility criteria	8
Recruitment	23	Information to be included in the CONSORT flow diagram	8
Withdrawal/ Follow-up	24a	Level of withdrawal, e.g., from intervention and/or from follow-up	8
	24b	Timing of withdrawal/lost to follow-up data	8
	24c	Reasons and details of how withdrawal/lost to follow-up data will be presented	8
Baseline patient characteristics	25a	List of baseline characteristics to be summarized	8-9
	25b	Details of how baseline characteristics will be descriptively summarized	8-9
Section 6: Analysis			
Outcome definitions		List and describe each primary and secondary outcome including details of:	9-13
	26a	Specification of outcomes and timings. If applicable include the order of importance of primary or key secondary end points (e.g., order in which they will be tested)	9-12
	26b	Specific measurement and units (e.g., glucose control, hbA1c [mmol/mol or %])	NA
	26c	Any calculation or transformation used to derive the outcome (e.g., change from baseline, QoL score, Time to event, logarithm, etc.)	9-13
Analysis methods	27a	What analysis method will be used and how the treatment effects will be presented	14-16
	27b	Any adjustment for covariates	15
	27c	Methods used for assumptions to be checked for statistical methods	15
	27d	Details of alternative methods to be used if distributional assumptions do not hold, e.g., normality, proportional hazards, etc.	14 (for 6-month survival)

	27e	Any planned sensitivity analyses for each outcome where applicable	14
	27f	Any planned subgroup analyses for each outcome including how subgroups are defined	15
Missing data	28	Reporting and assumptions/statistical methods to handle missing data (e.g., multiple imputation)	16
Additional analyses	29	Details of any additional statistical analyses required, e.g., complier-average causal effect ¹⁰ analysis	16
Harms	30	Sufficient detail on summarizing safety data, e.g., information on severity, expectedness, and causality; details of how adverse events are coded or categorized; how adverse event data will be analysed, i.e., grade 3/4 only, incidence case analysis, intervention emergent analysis	NA
Statistical software	31	Details of statistical packages to be used to carry out analyses	16
References	32a	References to be provided for nonstandard statistical methods	17
	32b	Reference to Data Management Plan	16-17
	32c	Reference to the Trial Master File and Statistical Master File	13 (analytic dictionary)
	32d	Reference to other standard operating procedures or documents to be adhered to	16-17

Taken from the paper: Gamble C, Krishan A, Stocken D, Lewis S, Juszczak E, Doré C, et al. Guidelines for the Content of Statistical Analysis Plans in Clinical Trials. JAMA. 2017;318(23):2337-43.

Abbreviations: CONSORT, Consolidated Standards of Reporting Trials; hbA1c, haemoglobin A1c; QoL, quality of life; SAP, statistical analysis plan.
